- slow (at least 5 minutes) intravenous infusion of ambroxol hydrochloride 30 mg twice daily is superior to placebo in change from baseline to day 3 and to the end of 1-week treatment of sputum viscosity score or expectoration difficulty score and of other indicators of mucolytic activity: individual sputum viscosity and expectoration difficulty scores, cough score, mucous color score and mucous volume.

Safety objectives

- Confirm that 1-week treatment with iv NAC 600 mg twice daily is safe and well tolerated.

Design:

Multicenter, randomized, rater- and patient-blind, placebo- and active-controlled, 3-arm parallel group clinical trial.

Subjects will be randomized to NAC or ambroxol or placebo in a 1:1:1 ratio.

The study will consist of a total of 4 core hospital visits and a follow-up call 2 weeks after end of treatment. If the patient is still hospitalized or if more convenient for the patient, the follow-up phone call can be replaced by a follow-up hospital visit.

Number of patients: A total of 333 patients will be randomized. This number includes 10% overage to allow for patients who discontinue the trial prematurely ("drop-outs") without contributing to the primary endpoint.

Trial duration: Approximately 8 months. The enrolment period will be approximately 7 months.

Duration of patient participation: Up to 4 weeks. Each patient will undergo a screening period of up to 1 week, a 1-week treatment period and a 2-week follow-up period.

Participating Countries: China

Number of Sites: Approximately 25

Population: **Inclusion criteria**

Patients will be enrolled in the trial if all of the following criteria are met:

1. Male or female adult (≥ 18 years old) hospitalized patients with respiratory tract diseases and abnormal mucus secretions such as: acute bronchitis, chronic bronchitis and exacerbations, emphysema, mucoviscidosis and bronchiectasis. Diagnostic criteria for these conditions are provided in [Annex 1](#)
2. Chinese ethnicity and/or Chinese
3. Signed the informed consent form before any study-related procedure
4. Sputum viscosity score ≥ 2 at randomization visit
5. Expectoration difficulty score ≥ 2 at randomization visit
6. Willingness and ability to comply with study procedures

Exclusion criteria

Patients will not be enrolled if one or more of the following criteria are met:

1. Intolerance or contra-indication to treatment with NAC or ambroxol or allergy to any component of the study treatments

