11.1.4. LABORATORY EVALUATIONS

Routine laboratory evaluations will be performed at Screening Visit (Visit 1) and Visit 4 and in case of premature discontinuation.

The blood samples must be collected after the 12-lead ECG has been performed.

The haematology and clinical chemistry parameters detailed in Table 1 will be analysed by the local hospital laboratory.

Subjects with clinically relevant impaired renal function, as defined by serum creatinine levels ≥ 3.0 x upper limit of normal at Visit 1 will not be randomized.

Subjects with clinically relevant impaired liver function, as defined by serum ALT and/or AST ≥ 3.0 x upper limit of normal at Visit 1 will not be randomized.

A dipstick urine pregnancy test for women of childbearing potential will be performed at Randomization Visit (Visit 2) and at Visit 4 and/or at unscheduled deterioration visit/premature discontinuation visit.

Female subjects who become pregnant during the trial must be withdrawn from the trial without delay and undergo the premature discontinuation visit; these patients are to be followed up to determine the outcome of the pregnancy. The Investigator is required to inform the Sponsor of a subject's pregnancy and the estimated date of delivery. Reporting requirements are outlined in [Section 18.10](#).

Clinical laboratory tests will be reviewed for results of potential clinical significance before Visit 2 to confirm patient's eligibility and during the trial, as appropriate. Clinically significant laboratory abnormalities arising at Visit 4 (or at premature discontinuation visit) are considered AEs. Where possible, a diagnosis should be ascribed to the abnormal lab test.

Table 1 CLINICAL LABORATORY EVALUATIONS

Hematology: at Screening Visit (Visit 1) and Visit 4 or premature discontinuation visit			
Hematocrit	Hemoglobin	Platelet count	Red blood cell count
White blood cell count and differential (neutrophils, lymphocytes, monocytes, eosinophils and basophils)			
Clinical Chemistry: at Screening Visit (Visit 1) and visit 4 or premature discontinuation visit			
BUN or UREA	Chloride	AST	
Creatinine	Uric acid	ALT	
Sodium	Amylase	γGT	
Potassium	ALP	Bilirubin (direct and total)	
Calcium			
Pregnancy Test: at Screening Visit (Visit 1), Visit 4 or premature discontinuation visit			
Urine β-hCG (dipstick)			

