equal to 0,79 and 0,77 for sputum viscosity and expectoration difficulty scores (change from baseline to the 1-week treatment) respectively and a correlation between the two endpoints equal to 0.31.

Assuming a drop-out rate of about 10% over one week of entry, a total of 333 patients will be randomized (i.e. 111 patients in the placebo group, 111 patients in the NAC group and 111 patients in the ambroxol group. The sample size calculations were performed using the Mediana package [22].

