20.4.8. SAFETY DATA

All safety endpoints will be summarised and analysed using the Safety Population.

Incidence of Treatment Emergent Adverse Events

The number and the percentage of subjects reporting TEAEs, treatment emergent SAEs, severe TEAEs, TEAEs leading to discontinuation and TEAEs leading to death will be presented by treatment group, along with the number of events occurring.

TEAEs will be summarised also by System Organ Class and Preferred Term according to MedDRA; they will be additionally summarised by severity and relationship to treatment. A separate summary table will be provided for SAEs.

Only TEAEs, i.e. events with an onset date on or after the date of IMP start, will be included in the summary tables. Individual data listings will include all AEs recorded; a separate listing will be provided for treatment-emergent SAEs.

Vital Signs

Descriptive statistics for vital signs will be presented overall and by treatment.

Physical examination data

Descriptive statistics for physical examination data will be presented overall and by treatment.

Haematology and clinical chemistry

Haematology and clinical chemistry tests results will be converted to standard international units and summarised by treatment group using descriptive statistics for continuous variables. Summaries for change from Visit 1 will be also provided. Frequency of subjects with values appearing outside the central laboratory normal range will be reported by visit for each treatment group. All values appearing outside the laboratory normal range will be highlighted in listings.

12-lead Electrocardiogram

Descriptive statistics for ECG results will be presented overall and by treatment (normal, abnormal clinically non-significant, abnormal clinically significant).

Adherence and Exposure

Subject adherence will be summarised by treatment group presenting descriptive statistics and percentages of adherent subjects, i.e. with a least 80% of compliance.

The total number of doses of IMP taken by each subject, will be summarised as well.

If an AE has a partial or fully missing date, and it is unclear whether the AE is treatment-emergent, it will be assumed that it is. In the AEs analysis, when relationship to study drug is missing for a treatment-emergent adverse event it will be imputed to be drug related. More detail will be provided in the Statistical Analysis Plan (SAP).

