For 24-hour sputum collection, the baseline measurement will be the last available data captured on Visit 2 (Day 1) or the next day (Day 2). This is because the collection of sputum is to begin on Day 1 and lasts for 24 hours up until the same time the next day (Day 2). Therefore, the baseline sputum volume measurement may be after the first dose of IMP.

Scheduled and Unscheduled Assessments

The by-visit tables will only include the scheduled assessments, unless specifically stated otherwise. If more than one value is available for a given visit, the first valid observation will be used in summary tables, unless specifically stated otherwise, and all observations will be presented in listings.

Unscheduled assessments will be included in listings, but not in summary tables.

Detection of Outliers

Any outliers that are detected during the review of the data before database lock will be investigated. If necessary, queries will be issued to Investigators, to either correct or confirm the outlier.

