4.10.4 Laboratory Evaluations

Laboratory evaluations will include Hematology, Clinical Chemistry (biochemistry), and Pregnancy test. Lab value will be converted to standard unit.

Quantitative laboratory measurements reported as '< X', i.e. below the lower limit of quantification (BLQ), or '> X', i.e. above the upper limit of quantification (ULQ), will be converted to X for the purpose of quantitative summaries, but will be presented as recorded, i.e. as '< X' or '> X' in the listings.

The evaluations of hematology and clinical chemistry (biochemistry) will be performed at Screening Visit (Visit 1) and Visit 4 and in case of premature discontinuation.

A dipstick urine pregnancy test for women of childbearing potential will be performed at Randomization Visit (Visit 2) and at Visit 4 and/or at unscheduled deterioration visit/premature discontinuation visit.

The parameters of hematology, clinical chemistry(biochemistry) and pregnancy test are presented in the following table.

Hematology:			
Hematocrit	Hemoglobin	Platelet count	Neutrophils
Lymphocytes			
Eosinophils	Basophils		
Clinical Chemistry(biochemistry):			
BUN	Chloride	AST	
Creatinine	Uric acid	ALT	
Sodium	Amylase	γGT	
Potassium	ALP	Bilirubin (direct and total)	
Calcium	UREA		
Pregnancy Test:			
Urine β-hCG (dipstick)			

The following summaries will be provided:

- A summary of hematology observed values at Visit 1 and Visit 4, and the changes from Visit 1 for each laboratory parameter by treatment group
For the continuous parameters, it will be summarized using the descriptive statistics. For the categorical parameters, a shift table of the test results at Visit 4 compared to the test results at Visit 1 will be provided
- A summary of clinical chemistry (biochemistry) observed values at Visit 1 and Visit 4, and the changes from Visit 1 for each laboratory parameter by treatment group
- A summary of urine Pregnancy Test observed values at Visit 1 and Visit 4
- A shift table of the pregnancy test results at Visit 4 compared to the pregnancy test results at Visit 2
- Summary of subjects with values outside central laboratory normal range by visit for each treatment group (Safety Population)

The following listings will be provided:

- A by-subject listing of all laboratory data, in which all values appearing outside the laboratory normal range will be highlighted
- A by-subject list of pregnancy test results

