4.10.5 Vital Signs and Physical Examination

Vital Signs

Vital Signs will be assessed at Screening Visit (Visit 1), Randomization Visit (Visit 2), Visit 3 and Visit 4 and/or at the unscheduled deterioration visit/premature discontinuation.

Vital signs include:

- heart rate (beats/minute),

- systolic and diastolic blood pressure, measured after at least 5 minutes in the supine position (mmHg)
- respiration rate (breaths/min)
- body temperature, measured under the arm pit (°C)

A summary of the observed values and changes from Visit 1 for each vital sign by treatment group and overall at each visit will be provided. Both raw values and changes from Visit 1 will be summarized using descriptive statistics.

A by-subject listing of vital signs will be provided.

Physical Examination

At Visit 1, Visit 2, Visit 3 and Visit 4, and/or at the unscheduled deterioration Visit/premature discontinuation, a physical examination of general body systems will be performed according to current medical standards and site practice. The general body systems include:

- Respiratory System
- Cardiovascular System
- Abdomen
- General Appearance
- Head and Neck
- Lymph Nodes
- Musculoskeletal System
- Nervous System
- Skin
- Endocrine System
- Ears, nose and throat
- Hematopoietic System
- Reproductive System
- Urinary System

The examination is to include a chest auscultation.

A summary of the number and percentage of subjects for each body system by category (normal, abnormal not clinically significant, and abnormal clinically significant), treatment group and overall at each visit will be provided.

A by-subject listing of physical examination will be provided.

4.10.6 12-Lead Electrocardiogram

12-lead electrocardiogram (ECG) recordings will be obtained at each study center using site machines at the Screening Visit (Visit 1) to verify the eligibility of the subject, and at Visit 4 or unscheduled deterioration visit.

ECG will be performed after obtaining vital signs. Prior to recording, the subject should be at rest for at least 5 mins.

ECG will be evaluated by the investigator/local medical staff and the recording will be reported in the eCRF as “normal”, “abnormal clinically significant” or “abnormal not clinically significant”.

A shift table of the ECG assessments at Visit 4 compared to the ECG assessments at Visit 1 by treatment group will be provided. When there are multiple assessments of ECG taken at a visit, the worst ECG finding will be used.

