For the non-inferiority tests, a sample of 100 patients per each active treatment group ensures sufficient disjunctive power (Monte Carlo disjunctive power = 82%) to detect non-inferiority between NAC and ambroxol in at least one co-primary end-point. These calculations are based on a one-sided non-inferiority t-test assuming a margin of non-inferiority equal to 0.30, standard deviation equal to 0.79 and 0.77 for sputum viscosity and expectoration difficulty scores (change from baseline to the 1-week treatment) respectively and a correlation between the two endpoints equal to 0.31.

Assuming a drop-out rate of about 10% over one week of entry, a total of 333 patients will be randomized (i.e. 111 patients in the placebo group, 111 patients in the NAC group and 111 patients in the ambroxol group).

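### The SAP's laboratory change tables and ECG shift table are defined at Visit 4 only, so exit results collected from early stoppers may have no place in them

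*SAP*

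**What the plan says.** **End-points.** Protocol 20.2 lists laboratory tests and the 12-lead ECG among the safety end-points. Protocol 20.4.8 adds: "All safety endpoints will be summarised and analysed using the Safety Population".

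**Collection.** Protocol 11.1.4, Table 1 gives the sampling times as "Clinical Chemistry: at Screening Visit (Visit 1) and visit 4 or premature discontinuation visit", with the same pattern for haematology. Protocol 10.11 asks for the Visit 4 evaluations, apart from dosing, at the premature-discontinuation visit. Protocol 10.10 asks for an ECG at the unscheduled deterioration visit, and for the full Visit 4 evaluations if the patient is then discontinued. The flow chart (Appendix 1) shows no bloods and no ECG at Visit 3.

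**Tables.** SAP 4.10.4 plans "A summary of hematology observed values at Visit 1 and Visit 4, and the changes from Visit 1 for each laboratory parameter", and chemistry likewise. SAP 4.10.6 plans "A shift table of the ECG assessments at Visit 4 compared to the ECG assessments at Visit 1 by treatment group". The out-of-range summary in SAP 4.10.4 is by visit and does not name the visits.

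**General rules.** SAP 4.2 restricts by-visit tables to scheduled assessments in the absence of an explicit exception, and says: "Unscheduled assessments will be included in listings, but not in summary tables". The same section, like Protocol 20.4.1, also says that data from withdrawn patients are used up to withdrawal, again subject to exceptions.

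**Contrast with efficacy.** SAP 4.9.1.3 expressly brings premature-discontinuation measurements into the imputation of efficacy scores. No safety section has a matching rule.

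**The concern.** For a patient who stops early, the exit visit takes the place of Visit 4 as the only post-treatment blood sample and ECG. The tables are tied to Visit 4, and the section that governs them sends unscheduled results to listings. A programmer who follows the SAP literally would therefore leave collected exit results out of the change and shift tables. Another, relying on the withdrawn-patients rule, might include them. The same SAP could yield two different sets of safety tables.

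At stake is the arm-by-arm summary of two stated safety end-points in a trial whose safety objective is to confirm that intravenous NAC is safe and well tolerated. Patients may leave because of an adverse event or a deterioration (Protocol 16 and 10.10), so those without a Visit 4 value need not resemble those who have one.

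**Working it through.** **1. The plan's own figure.** Inputs are 100 evaluable patients per arm and three equal arms (Protocol 20.3, SAP 4.11), with the allowance stated as: "Assuming a drop-out rate of about 10% over one week of entry".

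- 100 / (1 − 0.10) = 111.1 per arm. The plan states 111; strict rounding up would give 112.
- 3 × 111 = 333, as stated.
- Allowance: 111 − 100 = 11 per arm, 3 × 11 = 33 in total, and 33/333 = 9.9%.

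**2. Where each exit result goes under the SAP.**

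| Exit result | Collected under | Post-baseline time point of the table | What SAP 4.2 implies |
|---|---|---|---|
| ECG at the unscheduled deterioration visit | Protocol 10.10 | Visit 4 | Listing only; the visit is itself called unscheduled |
| ECG at the premature-discontinuation visit | Protocol 10.11 | Visit 4 | Visit never classed as scheduled or unscheduled; withdrawn-data rule points to inclusion; no assigned place |
| Bloods at the premature-discontinuation visit | Protocol 10.11 and 11.1.4 | Visit 4 | Same |
| Bloods when a patient is discontinued at a deterioration visit | Protocol 10.10, referring to 10.11 | Visit 4 | Not stated which visit they belong to |
| Any exit blood value, out-of-range table | As above | By visit, none named | Not stated how it enters |

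The SAP 4.10.6 rule on taking the worst ECG applies to several recordings within one visit, so it does not carry an exit ECG into Visit 4.

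**3. How many patients.** The number without a Visit 4 value is 333 × the early-stopping proportion. Only the 10% comes from the plan; 5% and 15% are assumed, to show the range.

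- 5%: 333 × 0.05 = 16.7, about 17.
- 10%: 333 × 0.10 = 33.3, about 33, or 11 per arm. The Visit 4 tables then rest on about 300 of 333 patients.
- 15%: 333 × 0.15 = 50.0, about 50.

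At each rate this is an upper limit on omitted results, because a patient with no exit test has nothing to add.

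**4. Direction of any bias.** Let s be the share of patients with an omitted exit result, c the abnormality rate in completers and r the rate in early stoppers. The Visit 4 table shows c. Including exit values gives (1 − s)c + s·r, so the table is off by s(r − c). The documents give neither c nor r. With s = 0.10 and an assumed c = 5%:

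| Assumed r | Rate with exit values: 0.9 × 5% + 0.1 × r | Rate shown at Visit 4 |
|---|---|---|
| 0% | 4.5% | 5.0% |
| 5% | 5.0% | 5.0% |
| 10% | 5.5% | 5.0% |
| 20% | 6.5% | 5.0% |
| 30% | 7.5% | 5.0% |

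The sign depends on whether r exceeds c, which the documents do not settle.

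**The case against.** The SAP nowhere says that premature-discontinuation results are excluded. Only the deterioration visit carries the unscheduled label. The premature-discontinuation visit has its own flow-chart column, and the SAP 4.2 rule on withdrawn patients favours using its data. Much of the clinical content is also captured elsewhere. Clinically significant laboratory abnormalities at that visit are adverse events (Protocol 11.1.4), as are clinically significant ECG abnormalities at either exit visit unless they relate to a condition present before consent (Protocol 11.1.6). All laboratory values are listed with out-of-range results highlighted, and all ECGs are listed. The tables are descriptive, and no safety hypothesis is tested. Finally, pooling exit values with day-7 values mixes lengths of exposure, so a Visit 4 table is a legitimate display.

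Most of this stands and limits the point. Exclusion is explicit only for the deterioration-visit ECG; for the premature-discontinuation visit the fault is an unresolved assignment. But the withdrawn-data rule yields to exceptions, and it does not say which column of a Visit 4 table an exit value belongs in. The adverse event tables do not show changes from Visit 1, out-of-range values judged not clinically significant, or the ECG category of abnormal but not clinically significant, which is part of the stated end-point. Listings give no comparison by arm. The mixing of exposure is answered by keeping both displays.

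**Conclusion.** The point holds in limited form and should be corrected. As written, the laboratory change tables and the ECG shift table have one post-baseline time point. Deterioration-visit ECGs fall outside the shift table, and premature-discontinuation results have no stated place. With no Visit 3 test to fall back on, an early stopper may be absent from these tables although a result exists. Under the 10% allowance that is at most about 33 of 333 patients, 11 per arm. Sample size, power and the efficacy analyses are unaffected.

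A reader might infer more, and the documents do not support it:

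- *That 10% of patients will have an omitted result.* The figure is a planning allowance ("This number includes 10% overage to allow for patients who discontinue the trial prematurely"), and patients lost to follow-up or withdrawing consent may have no exit test.
- *That every arm is made to look safer, or that an excess on NAC is hidden.* This needs abnormality rates, and for the second claim stopping rates by arm, that the documents do not give. Early stopping also covers discharge before day 7 and rescue mucolytic use, neither of which implies abnormal bloods or ECG.
- *That the Safety Population rule is contradicted.* A population defines who is eligible for a table; fewer patients with data at a time point does not breach it.
- *That Table 1 of the protocol defines the analysis value.* It is a collection schedule.
- *That the out-of-range table is also restricted to Visit 4.* It is by visit, and is only silent on exit values.

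**What to change.** In SAP 4.10.4 and 4.10.6, define an end-of-treatment value: Visit 4 or, if that is missing, the premature-discontinuation visit, or the deterioration visit at which the patient was discontinued. Use it for the laboratory change tables, the out-of-range counts and the ECG shift table, and state it as an exception to the SAP 4.2 rules on scheduled and unscheduled assessments. Show by arm how many patients contribute, and how many of those values come from an exit visit. Keep Visit 4-only columns beside it, since the combined value mixes exposure durations.

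The cost is about one sentence in each of two SAP sections and one derived visit in the safety datasets. It needs no new data and no change to patient management.

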4.10.5 Vital Signs and Physical Examination

Vital Signs

Vital Signs will be assessed at Screening Visit (Visit 1), Randomization Visit (Visit 2), Visit 3 and Visit 4 and/or at the unscheduled deterioration visit/premature discontinuation.

Vital signs include:

- heart rate (beats/minute),

- systolic and diastolic blood pressure, measured after at least 5 minutes in the supine position (mmHg)
- respiration rate (breaths/min)
- body temperature, measured under the arm pit (°C)

A summary of the observed values and changes from Visit 1 for each vital sign by treatment group and overall at each visit will be provided. Both raw values and changes from Visit 1 will be summarized using descriptive statistics.

A by-subject listing of vital signs will be provided.

Physical Examination

At Visit 1, Visit 2, Visit 3 and Visit 4, and/or at the unscheduled deterioration Visit/premature discontinuation, a physical examination of general body systems will be performed according to current medical standards and site practice. The general body systems include:

- Respiratory System
- Cardiovascular System
- Abdomen
- General Appearance
- Head and Neck
- Lymph Nodes
- Musculoskeletal System
- Nervous System
- Skin
- Endocrine System
- Ears, nose and throat
- Hematopoietic System
- Reproductive System
- Urinary System

The examination is to include a chest auscultation.

A summary of the number and percentage of subjects for each body system by category (normal, abnormal not clinically significant, and abnormal clinically significant), treatment group and overall at each visit will be provided.

A by-subject listing of physical examination will be provided.

4.10.6 12-Lead Electrocardiogram

12-lead electrocardiogram (ECG) recordings will be obtained at each study center using site machines at the Screening Visit (Visit 1) to verify the eligibility of the subject, and at Visit 4 or unscheduled deterioration visit.

ECG will be performed after obtaining vital signs. Prior to recording, the subject should be at rest for at least 5 mins.

ECG will be evaluated by the investigator/local medical staff and the recording will be reported in the eCRF as “normal”, “abnormal clinically significant” or “abnormal not clinically significant”.

A shift table of the ECG assessments at Visit 4 compared to the ECG assessments at Visit 1 by treatment group will be provided. When there are multiple assessments of ECG taken at a visit, the worst ECG finding will be used.

A by-subject listing of 12-lead ECG will be provided.

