11.1.6. SAFETY EVALUATIONS

Adverse Events

AEs will be recorded by Investigator in the appropriate eCRF Section from Visit 1 (date of informed consent) to the follow-up phone all or visit occurring 2 weeks (± 3 days) after the last administration of the investigational medicinal product (IMP). At each contact (i.e. clinical visit or phone call), subjects will be asked in a non-leading manner if they experienced any AEs.

All AEs occurring from the day of the first IMP administration, i.e. Visit 2, until the end of the trial, i.e. follow-up phone call, will be considered as treatment emergent TEAEs.

For definitions and reporting of AEs and SAEs, see [Section 18](#).

12-lead electrocardiogram (ECG)

12-lead ECG recordings will be obtained at each study centre using site machines at the Screening Visit (Visit 1) to verify the eligibility of the subject, and at Visit 4 or unscheduled Deterioration visit.

ECG will be performed after obtaining vital signs. Prior to recording, the subject should be at rest for at least 5 mins.

ECG will be evaluated by the investigator/local medical staff and the recording will be reported in the eCRF as "normal", "abnormal clinically significant" or "abnormal not clinically significant".

Abnormalities of clinical significance recorded at Visit 1, Visit 4 or unscheduled deterioration visit/premature discontinuation visit which are not related to pre-exist medical condition before ICF signature will be reported as AEs. Repeat measurements will be performed if needed.

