4.2 General Presentation Considerations

Continuous data will be summarized in terms of the mean, standard deviation (SD), median, minimum, maximum and number of observations, unless otherwise stated. The minimum and maximum will be reported to the same number of decimal places as the raw data recorded in the database. The mean, median, lower quartile and upper quartile will be reported to one more decimal place than the raw data recorded in the database. The SD will be reported to two more decimal places than the raw data recorded in the database. In general, the maximum number of decimal places reported shall be four for any summary statistic.

Categorical data will be summarized in terms of the number of subjects providing data at the relevant time point (n), frequency counts and percentages. Any planned collapsing of categories will be detailed in the SAP text and the data displays.

Percentages will be presented to one decimal place. Percentages will not be presented for zero counts. Percentages will be calculated using n as the denominator. If sample sizes are small, the data displays will show the percentages, but any textual report will describe frequencies only.

Changes from baseline in categorical data will be summarized using shift tables where appropriate.

P-values greater than or equal to 0.001, in general, will be presented to three decimal places. p-values less than 0.001 will be presented as “<0.001”.

Confidence intervals will be presented to one more decimal place than the raw data.

The data from all sites will be pooled. Unless stated otherwise, all available data from withdrawn subjects will be included in the analysis up to the time of withdrawal.

All tests will be one-sided and performed at the significance nominal level of $\alpha = 0.025$.

Baseline for Efficacy and safety

Generally, baseline measurements are the last available data obtained prior to the first administration of investigational medicinal product (IMP) at Visit 2.

For sputum viscosity, expectoration difficulty, sputum color and cough, the last available data at Visit 2 (Day 1) within 2 hours after the first dose of IMP can be used for baseline if no data was obtained prior to the first dose of IMP.

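### SAP 4.10.6 applies its worst-ECG rule to Visit 1 as well, so the shift table can show a worsening from the last pre-dose ECG as no shift or even as an improvement

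*SAP*

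**What the plan says.** SAP 4.10.6 sets out the ECG output: "A shift table of the ECG assessments at Visit 4 compared to the ECG assessments at Visit 1 by treatment group will be provided". It then gives the rule for several tracings: "When there are multiple assessments of ECG taken at a visit, the worst ECG finding will be used". The rule is not limited to visits after dosing. The only other ECG output is a by-subject listing.

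SAP 4.2 has three general rules that bear on this:

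- The definition of baseline, which covers safety data as well as efficacy data: "Generally, baseline measurements are the last available data obtained prior to the first administration of investigational medicinal product (IMP) at Visit 2".
- Several values at one visit: "the first valid observation will be used in summary tables, unless specifically stated otherwise".
- Unscheduled records: "Unscheduled assessments will be included in listings, but not in summary tables".

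Protocol 11.1.6 foresees repeat ECGs: "Repeat measurements will be performed if needed". The flow chart in Protocol Appendix 1 has no ECG at Visit 2, so Visit 1 is the only planned ECG before dosing.

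**The concern.** Taking the worst finding is cautious at Visit 4 and the reverse at Visit 1. A worse reference leaves less room for a later finding to count as a worsening. Suppose a screening ECG is abnormal, the repeat before dosing is normal, and the Visit 4 ECG is abnormal in the same class. Measured from the last pre-dose ECG, that patient worsened. Under 4.10.6 the table shows no shift. Conversely, a patient whose ECG had already returned to normal before dosing, and is normal at Visit 4, appears to have improved on treatment.

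The 12-lead ECG is a named safety end-point (Protocol 20.2), and the shift table is its only planned tabulation in the SAP. The SAP also leaves unclear whether the ECG sentence replaces the 4.2 baseline definition or only its first-valid-value default, so two programmers could build different Visit 1 columns.

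**Working it through.** The plan gives no figure to reproduce. The check is to apply the written rule to every possible pattern.

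**Inputs.** Three ordered ECG classes (Protocol 11.1.6 and SAP 4.10.6): normal (N), abnormal not clinically significant (NCS), abnormal clinically significant (CS). Take a patient with a first ECG and a repeat at Visit 1, and one ECG at Visit 4. That gives 3 × 3 × 3 = 27 patterns.

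**Definitions.** A worsening is a Visit 4 class above the repeat, which is the last pre-dose value (SAP 4.2). Under SAP 4.10.6 the reference is the worse of the two Visit 1 ECGs. There are 3 combinations of repeat and Visit 4 that worsen (N to NCS, N to CS, NCS to CS), each with 3 possible first ECGs, so 9 patterns:

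| First, Visit 1 | Repeat, Visit 1 | Visit 4 | From last pre-dose ECG | Under SAP 4.10.6 |
|---|---|---|---|---|
| N | N | NCS | N to NCS | N to NCS |
| N | N | CS | N to CS | N to CS |
| NCS | N | NCS | N to NCS | NCS to NCS, no shift |
| NCS | N | CS | N to CS | NCS to CS |
| CS | N | NCS | N to NCS | CS to NCS, improvement |
| CS | N | CS | N to CS | CS to CS, no shift |
| N | NCS | CS | NCS to CS | NCS to CS |
| NCS | NCS | CS | NCS to CS | NCS to CS |
| CS | NCS | CS | NCS to CS | CS to CS, no shift |

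**Result.** Five of the 9 still show as worsening. Four do not: three as no shift and one as an improvement. With the last pre-dose ECG as reference and the worst finding kept at Visit 4, all 9 show. If worsening is instead measured from the first Visit 1 ECG, the written rule again hides 4 of 9. With a single Visit 1 ECG it hides none.

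**How many patients.** The documents give no rates, so this is only an illustration, for the NCS, N, NCS pattern. Assume a share r of patients has a Visit 1 repeat, a share t of those repeats clears a transient NCS finding, and a share q has NCS at Visit 4 independently of that. Hidden worsenings per arm of 111 are 111 × r × t × q:

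- Low end: 111 × 0.02 × 0.25 × 0.05 = 0.03.
- High end: 111 × 0.20 × 0.75 × 0.20 = 3.3.

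The share of new NCS findings hidden is r × t, from 0.02 × 0.25 = 0.5% to 0.20 × 0.75 = 15%. If patients with a transient finding are more prone to a later one, independence fails and the figures rise.

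**The case against.** The best defence is that a specific rule may override a general one. SAP 4.2 introduces its baseline definition as a general one and lets its several-values rule yield to stated exceptions. The ECG table is set against Visit 1 and does not use the word baseline. Laboratory values and vital signs are compared with Visit 1 too. This stands in part. A reader might infer a flat contradiction within the SAP, but the wording does not support that. It is an unexplained departure from the general rule.

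Second, the worst-finding rule is not the only cause. If the first tracing is abnormal and the repeat normal, the first-valid-value default would give the same reference. A repeat recorded as unscheduled would stay out of summary tables altogether. This also stands, and it means that deleting the ECG sentence would not cure the problem.

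Third, there are backstops. Under Protocol 11.1.6, clinically significant findings at Visit 4 are reported as adverse events unless related to a condition that predates consent. The listing shows the ECGs. The Visit 1 ECG is taken at "the Screening Visit (Visit 1) to verify the eligibility of the subject", so CS tracings there should be uncommon in randomised patients. These points stand and leave mainly new NCS findings at risk, which the adverse event rule does not cover.

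Finally, worst at both visits is at least symmetric, whereas last against worst leans towards showing worsening. That is true, but it is the cautious direction for a safety table.

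**Conclusion.** The point holds, at low severity. The Visit 1 side of the ECG shift table takes the worst finding, and when Visit 1 ECGs disagree this can turn a worsening from the last pre-dose ECG into no shift or an improvement. It rests on reading the rule as covering any visit, which is what the sentence says, and on discordant repeats occurring at Visit 1. The number of patients affected is unknown and probably small.

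Three stronger readings are not supported:

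- A reader might infer that abnormalities arising on treatment vanish from the table. They do not. The Visit 4 finding stays and only its Visit 1 class changes, so the Visit 4 distribution by arm is unaffected.
- A reader might infer that the rule pulls the arms together. Visit 1 precedes randomisation and the rule is the same in all arms, so false improvements are not arm-specific. Hidden worsenings could thin out an excess in the worsening cells if one existed, but the documents give nothing from which to size that, and no test is planned.
- A reader might multiply an assumed repeat rate by 111 and call the result lost worsenings. That counts patients exposed to masking and leaves out the chance of an abnormal Visit 4 ECG.

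The efficacy analyses and error rates are untouched.

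**What to change.** In SAP 4.10.6, state that the Visit 1 column uses the last ECG before the first dose of IMP, including a repeat recorded as unscheduled, and that the worst-finding rule applies to post-dose ECGs only. The clause on unscheduled repeats is needed because SAP 4.2 would otherwise exclude them and leave the superseded tracing as the reference.

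The cost is one sentence and a small programming change, with no new data. The price is the slight tilt towards showing worsening noted above. If the blind has already been broken, provide the corrected table as an addition marked post hoc, as Protocol 20.4.1 requires.
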